11.2.1.5 Mean change in mean arterial pressure (MAP) averaged over Weeks 8-12

Mean Arterial Pressure (MAP) will be calculated for each subject using the following formula: $MAP = (2/3) * DBP + (1/3) * SBP$.

Mean change from baseline in MAP will be analyzed and compared between the 2 treatment groups using an MMRM model with baseline MAP as a covariate, treatment group, visit, interaction of visit and treatment group, and above-mentioned stratification factors as fixed effects. The same strategy as that used in MMRM for Hb will be used to choose variance covariance structure. Data up to visit of Week 52 will be included in the model. The estimates for difference of MAP averaged over Weeks 8 to 12 between the two treatment groups will be generated from an estimate statement from Visit Week 8 to 12. Non-inferiority margin for the difference between groups is 1mmHg. Superiority will be declared if the upper bound of the 2-sided 95% confidence interval of the difference between roxadustat and ESA (roxadustat – ESA) is below 0.

11.2.1.6 Time to first exacerbation of hypertension over Week 28 to 52

Subject with exacerbation of hypertension is defined as meeting the following criterion:

Increase in blood pressure: An increase from baseline of ≥ 20 mm Hg systolic BP and sBP ≥ 170 mmHg or an increase from baseline of ≥ 15 mm Hg diastolic BP and dBP ≥ 100 mmHg. Increases from baseline in blood pressure are considered as confirmed by taking the mean of triplicates.

An exacerbation of hypertension is defined as an increase from baseline of ≥ 20 mm Hg systolic BP and sBP > 170 mmHg or an increase from baseline of ≥ 15 mm Hg diastolic BP and dBP > 100 mmHg).

Time to an exacerbation of hypertension in blood pressure will be analyzed and compared between the 2 treatment groups using the Cox Proportional Hazards model adjusting for baseline stratification factors. Both Non-inferiority and Superiority of roxadustat vs. ESA will be tested. The Non-inferiority margin for the difference between groups is 1.3 and the superiority margin for the difference between groups is 1. Subjects will be censored at the time of the last available blood pressure if an increase in blood pressure does not occur.

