### 1.4.2.1 Studies in Subjects with NDD-CKD

Data from a 4-week dose ranging study in anemic CKD subjects not on dialysis (Study FGCL-SM4592-017) showed that roxadustat promotes erythropoiesis at lower doses in CKD subjects than in healthy volunteers. With roxadustat 0.7 mg/kg TIW dosing, mean Hb increased by 1.0 g/dL over a 6-week period in anemic CKD subjects who completed 4 weeks of dosing; more robust mean Hb increases of 2.0 to 2.3 g/dL occurred at roxadustat doses of 1.5 and 2.0 mg/kg TIW, respectively. Hemoglobin responder (Hb increase of  $\geq 1.0$  g/dL) rates were 62%, 60%, 91%, and 100% in the roxadustat 0.7, 1.0, 1.5, and 2.0 mg/kg TIW cohorts, respectively. The Hb responses were also robust at higher roxadustat doses (1.5 to 2.0 mg/kg) in the BIW dosing groups. With the additional criterion that Hb achieve a level of  $\geq 11$  g/dL as well as

increasing by  $\geq 1.0$  g/dL, the Hb responder rate with roxadustat 2.0 mg/kg was 89% and 91% in with BIW and TIW dosing, respectively. The rapid rates of rise in Hb with roxadustat treatment were not accompanied by elevations in blood pressure (BP), as has been reported with ESA treatment (Eschbach, 1989).

Data from 16- to 24-week treatment Phase 2b study in CKD subjects not on dialysis (Study FGCL-4592-041) showed that absolute and weight-based doses of roxadustat, administered TIW and BIW, effectively corrected Hb levels to a Hb target of 11 g/dL (range of 11 to 13 g/dL in 96 subjects and 10.5 to 12.0 g/dL in 48 subjects). Dose-response trends suggested that starting doses of 1.0 to 1.6 mg/kg roxadustat administered TIW are appropriate to correct Hb levels during 4 weeks of treatment in nondialysis CKD subjects. Roxadustat was also effective in maintaining Hb level following anemia correction.

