### 7.2 Secondary Endpoints

- **US (FDA) submission:** The proportion of subjects who achieve a Hb response at two consecutive visits during the first 24 weeks of treatment, without rescue therapy within 6 weeks prior to the Hb response.

A Hb response is defined, using central laboratory values, as

- Hb  $\geq 11.0$  g/dL and a Hb increase from baseline by  $\geq 1.0$  g/dL in subjects whose baseline Hb  $> 8.0$  g/dL, or
- Increase in Hb  $\geq 2.0$  g/dL in subjects whose baseline Hb  $\leq 8.0$  g/dL

- **Ex-US submission:** Mean Hb change from baseline to the average level during the Evaluation Period, defined as Week 28 until Week 36 without rescue therapy within 6 weeks prior to and during the evaluation period. This analysis will be based on the PPS population.

Both, US and ex-US Submissions:

- Average monthly IV iron use per subject during the Treatment Period. Mean change in low-density lipoprotein (LDL) cholesterol averaged over Weeks 12 to 24.

- Blood pressure effects:
  - Proportion of subjects with exacerbation of hypertension, meeting at least one of the following criteria:
    - Increase in BP: An increase from baseline of  $\geq 20$  mm Hg systolic BP and sBP  $>170$  mmHg, or an increase from baseline of  $\geq 15$  mm Hg diastolic BP and dBP $>100$  mmHg. Increases from baseline in blood pressure must be confirmed by repeat measurement.
  - Time to an increase in BP as defined above.
  - Mean change in mean arterial pressure (MAP) averaged over Weeks 8 to 12.
- Time to achieve first Hb response as defined by the primary endpoint (ex-US) (which is the secondary endpoint for the US [FDA]).

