This efficacy endpoint will be analyzed using a mixed model of repeated measures (MMRM) with Hb baseline value as covariate and treatment group and randomization stratification factors as fixed effects and MI ANCOVA as sensitivity analysis for Ex-US submission.

This null hypothesis will be rejected if the two-sided 95% CI for the difference of least square means from the mixed model is above -0.75 g/dL.

Hb values under the influence of a rescue therapy within 6 weeks prior to and during this 8-week evaluation period will be censored in the analysis.

- The average monthly iron use will be compared between the 2 treatment groups using an ANCOVA model with baseline iron replete as a covariate, and treatment group and randomization stratification factors as fixed effects. Superiority will be declared if the lower bound of the two-sided 95% CI of the difference between epoetin alfa and roxadustat exceeds zero.
- Mean change from baseline in LDL cholesterol averaged over Weeks 12 to 24 will be analyzed using an MMRM model with baseline LDL cholesterol as a covariate and treatment group, visit, visits by treatment arm, and randomization stratification factors as fixed effects. Superiority will be declared if the lower bound of the two-sided 95% CI of the difference between epoetin alfa and roxadustat exceeds zero.

- Proportion of subjects with exacerbation of hypertension, meeting at least 1 of the following criteria will be analyzed using CMH model adjusting for treatment group and stratification factors
  - Increase in blood pressure: An increase from baseline in systolic blood pressure (sBP) of  $\geq 20$  mm Hg and sBP  $> 170$  mmHg or an increase from baseline in diastolic blood pressure (dBP) of  $\geq 15$  mm Hg and dBP  $> 100$  mmHg. Increases from baseline in blood pressure must be confirmed by repeat measurement.

Noninferiority of roxadustat vs. epoetin alfa will be tested. Non-inferiority will be declared if the upper bound of the two-sided 95% CI of the hazard ratio is less than 1.3.

- Time to an increase in blood pressure (defined as an increase from baseline of  $\geq 20$  mm Hg systolic BP and sBP  $> 170$  mmHg or an increase from baseline of  $\geq 15$  mm Hg diastolic BP and dBP  $> 100$  mmHg). Time to an increase in blood pressure will be analyzed using the Cox Proportional Hazards model adjusting for treatment group and randomization stratification factors. Superiority of roxadustat vs. epoetin alfa will be tested.

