4.3 SECONDARY EFFICACY ENDPOINTS

The secondary efficacy endpoints are for both US and Ex-US submissions unless specified otherwise:

US (FDA submission): The proportion of subjects who achieve a Hb response at two consecutive visits with at least 5 days apart during the first 24 weeks of treatment, without rescue therapy within 6 weeks prior to the Hb response. This analysis will be based on the ITT Population.

A Hb response is defined, using central laboratory values, as

- Hb ≥ 11.0 g/dL and a Hb increase from baseline by ≥ 1.0 g/dL in subjects whose baseline Hb > 8.0 g/dL, or
- Increase in Hb ≥ 2.0 g/dL in subjects whose baseline Hb ≤ 8.0 g/dL

Ex-US submission: Mean Hb change from baseline to the average level during the Evaluation Period, defined as Week 28 until Week 36 without rescue therapy within 6 weeks prior to and during the evaluation period. This analysis will be based on the PPS population.

- The time to achieve the first hemoglobin (Hb) response defined by the primary endpoint for Ex-US or the first secondary efficacy endpoint for the US submission.
- Proportion of patient exposure time (months) with Hb ≥ 10 g/dL during Weeks 28-52, similarly analysis for the period between Weeks 28 - 36
- Mean change from baseline in Low-density lipoprotein (LDL) cholesterol averaged over Weeks 12-24
- Mean change from baseline in Hb levels between Weeks 18 to 24 in patients whose baseline hs-CRP $>$ ULN
- Average monthly IV iron use per subject during weeks 28-52
- Time to first RBC transfusion during the treatment
- Mean change in mean arterial pressure (MAP) averaged over Weeks 8-12

- Time to first exacerbation of hypertension (defined as [systolic BP ≥ 170 mmHg AND systolic BP increase from BL ≥ 20 mmHg] or [diastolic BP ≥ 110 mmHg AND diastolic BP increase from BL ≥ 15 mmHg]) during weeks 28 to 52

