 - Proportion of subjects achieving LDL target of <100 mg/dL averaged over Weeks 12-24 of treatment.
- **Blood Pressure Effect:**
 - Time to an exacerbation of hypertension over weeks 28-52, meeting at least 1 of the following criteria: Increase in blood pressure: An increase from baseline of ≥ 20 mm Hg systolic BP and sBP >170 mmHg or an increase from baseline of ≥ 15 mm Hg diastolic BP and dBP >100 mmHg.
 - Proportion of subjects achieving blood pressure treatment goal in ESRD subjects (pre dialysis systolic BP <140 mmHg and diastolic BP <90 mmHg) averaged over Weeks 12-28.
- **Health Related Quality of Life (HRQoL) and EQ-5D-5L Benefits of Anemia Therapy:**

Mean change averaged over Weeks 12, 36 and 52 of treatment including those listed below.

 - Vitality Sub-score of SF-36:
 - In FAS subjects with baseline Vitality Sub-score below 50.
 - In all FAS subjects.
 - Physical Functioning Sub-scores of SF-36:
 - In FAS subjects with baseline *Physical Functioning Sub-scores* below 40.
 - In all FAS subjects.
 - Anemia Subscale (“Additional Concerns”) of Functional Assessment of Cancer Therapy-Anemia (FACT-An) Scores:
 - In FAS subjects with baseline subscale scores below 55 (generally associated with fatigue).
 - In all FAS subjects.

- Total FACT-An Scores:
 - In FAS subjects with baseline FACT-An scores below 135
 - In all FAS subjects.
- EQ-5D-5L Scores and other QoL Measures/Other Component scores of SF-36: In all FAS subjects.
- **Hepcidin, Iron, C_Hr and HbA1c:**
 - Change from baseline in serum hepcidin at each of the selected time points (e.g., Weeks 4, 12, 20, 44 and every 8 weeks onwards)
 - Change in serum iron from baseline to Week 28
 - Change in TSAT from baseline to Week 28
 - Change from baseline in serum ferritin at each of the selected time points, total and sub-grouped by baseline values of, ≥ 400 ng/mL, 400 to 100 ng/mL, and <100 ng/mL.
 - Change from baseline in TSAT at each of the selected time points, total and sub-grouped by baseline values of $\geq 40\%$, 40% to 20%, and $<20\%$.
 - Serum iron at each of the time points tested
 - Change from baseline in C_Hr at each of the selected time points (e.g., Weeks 4, 8, 12, 20, 28, 36 and every 8 weeks onwards)
 - Proportion of patients with C_Hr $>$ LLN at each timepoint tested: Weeks 4, 8, 12, 20, 28, 36, and every 8 weeks onwards)

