11 EFFICACY ANALYSES

Efficacy analysis will be conducted on the ITT and FAS for US (FDA) submission and analysis for non-inferiority on the PPS population and analysis for superiority on FAS population for EU regulatory submission.

The **Efficacy Emergent Period** is defined as the evaluation period from the Analysis date of first dose intake up to 7 days after the Last Dose of study drug or EOT Visit, whichever occurs first. This period will be used as reference period for the time to event analyses related to efficacy endpoints, unless specified otherwise.

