11.2 ANALYSIS OF SECONDARY ENDPOINTS

The secondary endpoints are for both U.S. and Ex-U.S. submission unless otherwise specified. Once the primary hypothesis has been rejected for the primary endpoint, the secondary endpoints in the order that was specified in section 4.3 will be tested using a fixed sequence testing procedure, in order to maintain the overall two-sided type I error of 0.05. If p-value from a test is < 0.05, the claim of superiority or non-inferiority will be considered successful and the test will progress to the next comparison in sequence as follows.

Table 5 Key Secondary Endpoints Fixed Sequence Testing Procedure

Test	Variable	Comparison
1	Proportion of subjects who achieve an Hb response at two consecutive visits during the first 24 weeks of treatment, (U.S.) or the mean Hb change from baseline to the average level during the Evaluation Period, defined as Week 28 until Week 52 for Ex-U.S..	Non-inferiority of roxadustat versus EPO. The non-inferiority margin for the difference of responder analysis between groups is 0.15 The non-inferiority margin for the difference of average of Change in Hb values between groups is - 0.75 g/dL.
2	LDL cholesterol change from BL to the average of weeks 12 to 24.	Superiority of roxadustat versus EPO
3	Mean change from baseline in Hb levels between Weeks 18 to 24 in patients whose baseline CRP > ULN:	The non-inferiority with margin of - 0.75 of roxadustat versus EPO
4	Monthly IV iron (mg) use per subject during weeks 28 to 52.	Superiority of roxadustat versus EPO
45	Time to first RBC transfusion during the treatment.	Non-inferiority of roxadustat versus EPO with Non-inferiority margin of 1.8
5	Change from BL to the average MAP of weeks 8 to 12	Superiority of roxadustat versus EPO
6	Time to first exacerbation of hypertension (defined as [systolic BP \geq 170 mmHg AND systolic BP increase from BL \geq 20 mmHg] or [diastolic BP \geq 110 mmHg AND diastolic BP increase from BL \geq 15 mmHg]) during weeks 28 to 52	Superiority of roxadustat versus EPO & Non-inferiority with margin of 1.8

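### The SAP restricts the tested hypertension-exacerbation endpoint to Weeks 28-52 without giving a reason, so early events that the protocol endpoint counts are left out and their handling is undefined

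*SAP*

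**What the plan says.** **Protocol.** Section 7.2 lists "Time to an increase in BP as defined above" as a secondary endpoint for both submissions. Section 8.4.3.2 gives the method: "Time to an increase in blood pressure will be analyzed using the Cox Proportional Hazards model adjusting for treatment group and randomization stratification factors", with a superiority test. Neither place restricts the weeks. Both sections also carry a test of the proportion of subjects with an exacerbation, again without a window. Section 8.4.5 says that significant changes to the planned analyses will be highlighted in the SAP.

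**SAP.** Section 1 says the SAP is based on protocol Amendment 4. Section 4.3 ends its list of secondary endpoints with time to first exacerbation, closing "AND diastolic BP increase from BL ≥ 15 mmHg]) during weeks 28 to 52". Table 5 in section 11.2 places this last in the fixed sequence, for "Superiority of roxadustat versus EPO & Non-inferiority with margin of 1.8". Section 11.2.1.6 repeats the window in its heading: "Time to first exacerbation of hypertension over Week 28 to 52". The only other exacerbation endpoint, in section 4.4, has the same window: "Time to an exacerbation of hypertension over weeks 28-52, meeting at least 1 of the following criteria". The protocol's unwindowed proportion test is not in the SAP's secondary list.

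Section 11 defines the Efficacy Emergent Period, from first dose to 7 days after last dose or the EOT visit, whichever is first, and adds: "This period will be used as reference period for the time to event analyses related to efficacy endpoints, unless specified otherwise". Section 11.2.1.6 censors at the last available blood pressure. It states no time origin and no rule for subjects who have an exacerbation, or stop treatment, before Week 28.

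**The concern.** Three things follow from the window.

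1. **Early events do not count.** Correction of Hb starts on Day 1, and the sample-size section assumes that 80% respond within 24 weeks. Most of the correction phase therefore lies before Week 28. Protocol 1.4.2.1 reports that fast Hb rises on roxadustat came without blood pressure elevation and contrasts this with reports for ESAs. The early weeks are thus where the protocol's own reasoning would look for a difference.
2. **The comparison is no longer between the groups as randomised.** Subjects who stop before Week 28 contribute nothing, so the risk set is formed by what happened after randomisation.
3. **The result depends on an unstated rule.** Whether a subject with an earlier exacerbation is excluded or remains at risk changes the estimate.

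At stake is a formal superiority and non-inferiority claim on a named secondary objective (blood pressure). The loss is symmetric. An early excess on epoetin alfa would be hidden, which weakens the roxadustat superiority test. An early excess on roxadustat would also be hidden, which weakens the meaning of a non-inferiority claim.

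**Working it through.** The documents give no event rate, event count or power for this endpoint, so there is no stated figure to reproduce.

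**Share of the schedule left out.** Weeks 0-28 are 28/52 = 54% of year one. Blood pressure is taken at every visit. Post-baseline visits before Week 28 are Weeks 1-4 (4 visits) and Weeks 6-24 every two weeks (10 visits), 14 in all. Weeks 28-52 every four weeks give 7. So 14 of 21 scheduled measurements fall before the window.

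**Who can contribute.** The default on-treatment period ends at most 7 days after last dose. If section 11.2.1.6 were read as overriding that default, the last scheduled blood pressure would still be at the EOS visit, 4 weeks after EOT or ET. Later follow-up covers CV events of interest, vital status and hospitalisation. Early stoppers are out on either reading.

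**Size, under assumptions.** Let H be the control cumulative hazard to Week 28, HR_e the early hazard ratio, θ the variance of a gamma frailty, and the true late hazard ratio 1. If subjects with earlier events are excluded, the hazard ratio just after Week 28 is

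(1 + θH) / (1 + θH·HR_e), with H = [(1 − p)^(−θ) − 1]/θ for control incidence p by Week 28.

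- p = 20%, θ = 1: H = 1/0.8 − 1 = 0.25. For HR_e = 1.5 the ratio is 1.25/1.375 = 0.91; for HR_e = 2.0 it is 1.25/1.5 = 0.83.
- p = 30%, θ = 2: H = (1/0.49 − 1)/2 = 0.52, θH = 1.04. For HR_e = 1.5 the ratio is 2.04/2.56 = 0.80; for HR_e = 2.0 it is 2.04/3.08 = 0.66.
- θ = 0: the ratio is 1 for any p and HR_e.

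A Cox simulation (200,000 per arm, constant control hazard, 25% off treatment by Week 28 in both arms) covered p = 10-30%, θ = 0-2 and HR_e = 1.5-2.0. Selected rows:

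| p | θ | HR_e | HR Day 1-Week 52 | HR Weeks 28-52, earlier events kept | HR Weeks 28-52, earlier events excluded |
|---|---|---|---|---|---|
| 10% | 0 | 1.5 | 1.32 | 0.99 | 1.01 |
| 20% | 1 | 1.5 | 1.29 | 1.00 | 0.94 |
| 30% | 0 | 2.0 | 1.71 | 0.99 | 1.01 |
| 30% | 2 | 1.5 | 1.23 | 1.01 | 0.84 |
| 30% | 2 | 2.0 | 1.42 | 1.01 | 0.71 |

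Over the whole grid the Day 1-Week 52 ratio is 1.23-1.71. The windowed ratio is 0.97-1.01 with earlier events kept and about 0.71-1.01 with them excluded. In these scenarios about 68-84% of first events fall before Week 28; that share follows from the assumed hazards, not from any figure in the plan.

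**Conflicts within the same endpoint.**

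| Item | SAP 4.3 / Table 5 | SAP 11.2.1.6 |
|---|---|---|
| Non-inferiority margin | 1.8 (Table 5) | 1.3 |
| Systolic level (mmHg) | ≥170 | ≥170 in one sentence, >170 in another |
| Diastolic level (mmHg) | ≥110 | ≥100 in one sentence, >100 in another |

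Protocol 7.2 uses >170 and >100.

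**The case against.** **Early blood pressure is not unexamined.** Table 5 tests superiority on mean arterial pressure at Weeks 8-12 immediately before the hypertension test. If roxadustat raised blood pressure early, the sequence would probably stop there. SAP 11.3.6 compares blood pressure goal attainment over Weeks 12-28 and mean arterial pressure over Weeks 20-28. SAP 12.3 counts high values at any post-baseline visit, and hypertensive emergencies are adjudicated. This stands and lowers the stakes. It does not replace the missing comparison: a mean over a few visits is not an exacerbation endpoint, the vital-signs table is descriptive, and none of these is a between-arm exacerbation test from Day 1.

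**The SAP may choose a window.** Its default period allows exceptions, and a maintenance-phase question is legitimate. That also stands, but the departure from the protocol's tested endpoint should then be explained, as protocol 8.4.5 requires.

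**The protocol's reasoning places any early effect on the comparator.** On that evidence the window works against roxadustat. The passage concerns non-dialysis subjects, however, and a hidden difference is a defect in either direction.

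**A stronger reading is tempting.** A reader might infer from the word *first* that only subjects event-free at Week 28 are compared, so that an arm with more early hypertension would later look protective. The SAP states no such exclusion; *first* can equally mean first within the window. Even with exclusion and heterogeneous risk, false superiority is uncommon. With θ of 1-2, H of 0.3-0.5, HR_e of 1.5, 30% yearly dropout and 300-600 per arm, simulation declares it in roughly 5-16% of trials. Passing non-inferiority despite the early excess is the likelier error: about 24-59% at a margin of 1.3 and 65-98% at 1.8.

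**Conclusion.** The concern holds as an unexplained narrowing of a hypothesis-tested endpoint, with its time origin and its handling of earlier events and discontinuations left undefined. The test omits most of the correction phase and rests on a subset selected after randomisation. Under the assumed rates, an early excess that shows as a hazard ratio of about 1.2-1.7 from Day 1 becomes about 1.0 in the window when subjects with earlier events are kept.

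Reversal into apparent protection is not established. It needs exclusion of those subjects together with heterogeneous risk, or unequal dropout driven by events, which was not simulated. Nor do the documents support saying that most first events are lost, since they give no event rate. All sizes here rest on assumed incidence, frailty and dropout.

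The endpoint is last in the sequence and early blood pressure is partly covered elsewhere, so this should be corrected but does not threaten the primary analyses.

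**What to change.** In SAP 4.3, Table 5 and 11.2.1.6, test time to first exacerbation with the time origin at first dose, over the Efficacy Emergent Period. This restores the protocol's unrestricted start. If follow-up is capped at Week 52, say that the cap is an SAP choice; the protocol has none.

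Keep Weeks 28-52 as a supportive summary, and state there whether subjects with an earlier exacerbation are excluded or kept, and how those who stop before Week 28 are treated. Record the change from the protocol and its reason.

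In the same edit, reconcile the non-inferiority margin (1.8 against 1.3) and the systolic and diastolic thresholds across SAP 4.3, Table 5, 11.2.1.6 and the protocol.

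The cost is SAP wording and a date filter, since blood pressure is already collected at every visit. The drawback is that the estimate then mixes the correction and maintenance phases, which the supportive summary helps to separate.
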